10.1.3.3 Follow-Up Period (Day 85 to 98)

During the follow-up period, the study center will have 1 phone visit (2 weeks after End of Treatment) to capture information on any AEs which occur after the End of Treatment visit, using the phone visit script.

10.1.3.4 Early Termination

The study may be terminated at an individual study center if it becomes apparent that subject enrollment is unsatisfactory with respect to quality and/or quantity. Study centers may also be closed if they prove to be unable to comply with the requirements of the protocol or GCP, or data recording is inaccurate and/or incomplete. If the study is terminated in an individual study center for any reason, the investigator must make every effort to follow-up all subjects as planned according to the protocol. Replacement of study centers is allowed and new study centers may be initiated. An initiative for study center closure or study termination can be taken at any time either by Ovid Therapeutics

Inc. or by the investigator, provided there is reasonable cause and sufficient notice is given in advance of the intended termination.

See Section 13 for early withdrawal from study. For early withdrawal, subject should follow Week 12 study visit schedule of assessment for safety measure which include medical history, clinical assessment, ABC-C irritability subscale, physical examination, clinical lab test, serum pregnancy test, concomitant medications. Efficacy assessments do not need to be completed.

10.2 Discussion of Study Design

Neither the investigators nor the subjects will be aware of the treatment assignments, to minimize any subjective or unrecognized bias in reporting. Placebo will be used as the comparator.

Based on the potential reproductive effects observed in pre-clinical studies, pre-menopausal females who have a positive pregnancy test at the screening or baseline visits, or those who are not able to use an effective method of contraception (with abstinence being an accepted method), will be excluded from the study.

Pre-clinical and clinical data suggest that the doses prescribed in this study will likely be therapeutically relevant and well-tolerated.

A variety of scales will be employed for the exploratory assessment of safety and exploratory efficacy endpoints (Section 13).

10.3 Risk/Benefit Assessment

In adult subjects, the most common AEs occurring more frequently in OV101-treated subjects than in subjects on placebo have been dizziness, nausea, vomiting, somnolence, and headache. Most AEs have been mild to moderate severity. OV101 is generally tolerated better by males than females and has been generally safe and well tolerated in Phase 2 and 3 insomnia studies in adult subjects at doses up to 15 mg and in the elderly at doses up to 10 mg.

OV101 is rapidly absorbed and eliminated when given orally at doses of 10 to 40 mg. The maximum plasma concentration is reached after half to 1 hour, the elimination half-life is approximately 1.5 hours and there is no evidence of accumulation after 5 days of multiple dosing. Pharmacokinetic data from the adolescent PK study OV101-16-001 with a single 5 mg oral administration to adolescent male and female subjects with FXS or AS suggest the exposure of OV101 is comparable to young adult subjects given the same dose. The dosing recommendation for adolescents in this study is therefore the same as for adults.

Close monitoring of safety will be conducted throughout this study.

11. SELECTION OF SUBJECTS

11.1 Diagnosis and Main Criteria for Inclusion:

Adolescents and adults with a molecularly-confirmed diagnosis of AS will be eligible for inclusion in the study. See Section 10.1.3.1 for testing of individuals who do not have documentation of diagnosis.

After obtaining signed informed consent from the legally authorized representative (e.g. parent or caregiver) and assent as appropriate from the potential subject, an individual with AS will begin the study screening procedures to confirm eligibility. The screening procedures to confirm eligibility will include clinical and laboratory evaluation as well as all measurements to assess exploratory efficacy (sleep, motor function, and behavior).

Those who do not consent to the gene biomarker sampling will still be eligible to participate in the STARS study.

For those individuals not possessing documentation of a molecularly confirmed AS diagnosis, DNA samples will be obtained during the screening period to confirm the diagnosis of AS.

If a subject needs a repeat lab or additional lab to confirm eligibility the screening period may be extended.

11.2 Inclusion Criteria

A subject will be eligible for enrollment in the study if ALL of the following criteria apply:

1. Age \geq 13 years, \leq 49 years at the time of informed consent
2. Molecular confirmation of AS
3. Receiving a stable dose of concomitant medications such as anti-epileptic medication, gabapentin, clonidine, melatonin, trazadone, supplements, special diets for at least 4 weeks prior to Baseline; and able to maintain these throughout the duration of the study
4. Has a parent or caregiver capable of providing informed consent on behalf of the subject and able to attend scheduled study visits to participate in all assessments described in the protocol
5. Able to attend scheduled study visits and be willing to perform the required clinical evaluations
6. Able to ingest the study drug

7. Caregivers must agree not to post any subject's personal medical data related to the study or information related to the study on any website or social media site (e.g. Facebook, Twitter, etc.) until the study is completed

11.3 Exclusion Criteria

A subject will NOT be eligible for this study if any of the following criteria apply:

1. Non-ambulatory subjects (e.g. requiring a wheelchair) not able to perform the assessments of Motor Ability/Function
2. Poorly controlled seizures defined as > 3 seizures lasting less than 3 minutes per week or > 1 seizure episode lasting more than 3 minutes per week or as per medical monitor judgment
3. Concomitant cardiovascular or respiratory diseases of a degree that would limit participation in the study
4. Concomitant disease (e.g., gastrointestinal, renal, hepatic, endocrine or cardiovascular system disease) or condition or any clinically significant finding at screening that could interfere with the conduct of the study, or that would pose an unacceptable risk to the subject in this study
5. Any of the following laboratory abnormalities: total bilirubin >1.5 x upper limit of normal (ULN) (unless isolated Gilbert's syndrome), alanine aminotransferase or aspartate aminotransferase >2.5 x ULN; serum creatinine >1.2 x ULN; absolute neutrophil count <1.5 x 10⁹/L, platelets < 80 x10⁹/L, hemoglobin <80 g/L; TSH >1.25 x ULN or <0.8 x ULN
6. Pregnancy
7. Women of child-bearing potential who are not using a double-barrier method of contraception (e.g. condoms plus oral contraceptives), with abstinence being an accepted method
8. Concomitant use of minocycline, levodopa, zolpidem, zaleplon, eszopiclone, ramelteon or benzodiazepines for sleep, as well as, cannabinoid derivatives, and any other use of any investigational agent, device, and/or investigational procedure 4 weeks prior to Baseline and during the study
9. Allergy to OV101 or any excipients
10. At increased risk of harming self and/or others based on investigator assessment
11. Any condition or reason that in the opinion of the investigator, makes the subject unsuitable for enrollment
12. Inability of subject or caregiver to comply with study requirements

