3.2 Analysis Populations and Subgroups

3.2.1 Definition of Analysis Populations

Safety Analysis Set

The Safety Analysis Set consists of all subjects who received at least one dose of study drug. Subjects will be analyzed according to the treatment they actually received. The Safety Analysis Set will be the analysis set used for all safety analyses.

Intent-to-Treat Set

The Intent-to-Treat set (ITT) consists of all subjects who are randomized, whether or not study drug is received. Subjects will be analyzed according to their randomized group.

Full Analysis Set (also considered the modified Intent-to-Treat set)

The Full Analysis Set (FAS) or modified Intent-to-Treat set (mITT) consists of all randomized subjects who receive at least 1 dose of study drug, and have at least 1 efficacy evaluation after receiving study drug. Subjects will be analyzed according to their randomized group. The FAS will be the primary analysis set for efficacy analyses.

Per Protocol Set

The Per Protocol Set (PP) is a subset of the FAS that includes all subjects who complete the Week 12 visit and have no major protocol deviations that are deemed to impact efficacy. These violations include but are not limited to violations of inclusion/exclusion criteria deemed to impact efficacy, inadequate study drug compliance over the dosing period as determined from the dosing information in the eCRF, usage of prohibited concomitant medications, and incorrect randomization. Subjects will be analyzed according to their randomized treatment group. The PP set will be used for the analysis of the key efficacy endpoints only.

Prior to database lock and unblinding, there will be a meeting to review protocol deviations. The threshold for percent compliance that would be considered inadequate and would result in exclusion from the per protocol set will be determined in this meeting following review of the relevant compliance information. In addition to the deviations listed above, other relevant protocol deviations, like early termination of treatment, may be identified for review.

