6. LIST OF ABBREVIATIONS AND DEFINITION OF TERMS

[figure not shown]
| | |
|------------|--|
| ABC-C | Aberrant Behavior Checklist – Community |
| ██████████ | ██████████ |
| AE | Adverse event |
| AS | Angelman syndrome |
| ██████████ | ██████████ |
| β-hCG | beta-Human chorionic gonadotrophin |
| BID | Twice daily |
| ██████████ | ██████████ |
| CGI-I | Clinical Global Impression – Improvement |
| CGI-S | Clinical Global Impression – Severity |
| ██████████ | ██████████ |
| CI | Confidence interval |
| COA | Clinical outcomes assessment |
| CTCAE | Common Terminology Criteria for Adverse Events |
| D | Day |
| eCRF | Electronic case report form |
| EEG | Electroencephalogram |
| ██████████ | ██████████ |
| FAS | Full analysis set |
| FDA | Food and Drug Administration |
| FXS | Fragile X syndrome |
| GABA | Gamma-aminobutyric acid |
| GCP | Good clinical practice |
| ICF | Informed consent form |
| ICH | International Conference on Harmonization |
| IRB | Institutional review board |
| IWRS | Interactive Web Response System |
| MedDRA | Medical Dictionary of Regulatory Activities |
| MM | Medical Monitor |
| ██████████ | ██████████ |
| MMRM | Mixed model repeated measures |
| ██████████ | ██████████ |

| | |
|-------------|----------------------------------|
| PT | Preferred term |
| QD | Once daily |
| SAE | Serious adverse event |
| SAP | Statistical analysis plan |
| SAS | Statistical Analysis Software |
| | |
| | |
| SOC | System organ class |
| SOL | Sleep onset latency |
| SOP | Standard operating procedure |
| SS | Safety analysis set |
| TEAE | Treatment-emergent adverse event |
| TST | Total sleep time |
| UBE3A/Ube3a | Ubiquitin protein ligase E3A |
| ULN | Upper limit of normal |
| USA | United States of America |
| WASO | Wake after sleep onset |

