15.4 Laboratory Assessments

Blood samples will be collected for routine clinical laboratory safety evaluations. Study center staff can apply the best local practices to obtain a blood sample in this population.

Additional laboratory safety evaluations will be performed at other times, if judged to be clinically appropriate, or if the ongoing review of the data suggests a more detailed assessment of laboratory safety evaluations is required. Any changes to the scheduled times of laboratory safety tests will be agreed with [REDACTED] and Ovid Therapeutics Inc. and documented. The investigator will perform a clinical assessment of all laboratory safety data.

Laboratory parameters include electrolytes, lipids, glucose, renal, hepatic and pancreatic function tests, and hematology. A serum pregnancy test will be done for female subjects at the times noted in Table 1.

Table 3 lists the clinical chemistry and hematology tests planned for this study.

Table 3 Clinical Chemistry and Hematology Tests

| Clinical Chemistry | Hematology |
|---|------------------------|
| Albumin | Basophils (absolute) |
| Alkaline phosphatase | Eosinophils (absolute) |
| Alanine aminotransferase | Lymphocytes (absolute) |
| Aspartate aminotransferase | Monocytes (absolute) |
| Bicarbonate | Neutrophils (absolute) |
| Calcium | Basophils |
| Chloride | Eosinophils |
| Cholesterol | Hematocrit |
| Creatine kinase | Hematology slide |
| Creatine, enzymatic | Hemoglobin |
| Direct bilirubin | Lymphocytes |
| Glucose, random, serum | Monocytes |
| High density lipoprotein cholesterol | Neutrophils |
| Indirect bilirubin | Platelets |
| Lactate dehydrogenase | Red blood cells |
| Low density lipoprotein cholesterol, calculated | White blood cells |
| Phosphorous | - |
| Potassium | - |
| Sodium | - |
| Total bilirubin | - |
| Total protein | - |
| Triglyceride | - |
| Urea (blood urea nitrogen) | - |
| Uric acid | - |
| Total cholesterol | - |
| Magnesium | - |
| Thyroid stimulating hormone | - |

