17.2.2 Statistical Analysis Sets

The following 4 analysis sets will be included:

Safety Analysis Set

The Safety Analysis Set (SS) will consist of all subjects who receive at least one dose of study drug. Subjects will be analyzed according to the treatment they actually receive. The SS will be the primary analysis set for safety analyses.

Intent-to-Treat Set

The Intent-to-Treat set will consist of all subjects who are randomized, whether or not study drug is received. Subjects will be analyzed according to their randomized group.

Full Analysis Set

The Full Analysis Set (FAS) will consist of all randomized subjects who receive at least 1 dose of study drug, and have at least 1 efficacy evaluation after receiving study drug. Subjects will be analyzed according to their randomized group. The FAS will be the primary analysis set for efficacy analyses.

Per Protocol Set

The Per Protocol Set is a subset of the FAS that includes all subjects who complete the Week 12 visit, and have no significant protocol violations that are deemed to impact efficacy. These violations include but are not limited to violations of inclusion/exclusion criteria, less than 80% study drug compliance, and usage of prohibited concomitant medications. Further details will be provided in the SAP. Subjects will be analyzed according to their randomized group.

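### Exclusion criterion 5 sets the lower TSH limit as a multiple of the upper limit of normal, so read literally it excludes most people with a normal TSH

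*Combined protocol and SAP*

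**What the plan says.** Section 11.3 of the protocol opens with "A subject will NOT be eligible for this study if any of the following criteria apply". Criterion 5 then introduces its list with "Any of the following laboratory abnormalities", and the last item is "TSH >1.25 x ULN or <0.8 x ULN". The synopsis (Section 7) carries the same wording. ULN is spelled out within criterion 5 itself, and the abbreviation list in Section 6 gives it as "Upper limit of normal". That list has no entry for a lower limit of normal.

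TSH is a planned test: "Thyroid stimulating hormone" appears in Table 3 (Section 15.4), and laboratory tests are scheduled at Screening, Baseline, Week 6 and Week 12.

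On the analysis side, the protocol's Per Protocol Set (Section 17.2.2) requires "no significant protocol violations that are deemed to impact efficacy". The SAP (Section 3.2.1) names "violations of inclusion/exclusion criteria deemed to impact efficacy" and leaves the judgement to a meeting before database lock and unblinding.

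**The concern.** A two-sided thyroid criterion would normally have its ceiling tied to ULN and its floor tied to LLN. Here both are tied to ULN, so the floor falls inside the normal range, near its top. A mid-normal TSH then makes a subject ineligible under a list described as abnormalities.

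The documents do not show which reading sites followed, and both cause trouble.

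- **Literal reading.** Most euthyroid candidates fail screening, and those who pass have high-normal or mildly raised TSH. The disorder occurs in about 1 in 15,000 births, and Section 17.1 already allows for a shortfall to 20 subjects per group.
- **Presumed intent (a floor tied to LLN).** Most enrolled subjects would technically breach the written criterion. Section 19.1 does not let investigators depart from the protocol without an approved amendment, apart from immediate hazards and logistical or administrative changes.

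The wording also reaches past screening. Section 13.1.2 lets the investigator stop study drug if a subject develops a condition named in the exclusion criteria, and read literally that would cover a normal TSH at Week 6.

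**Working it through.** The plan states no figure on this point, so there is none to reproduce. The sample-size precision in Section 17.1 does not involve TSH: 1.96 x sqrt(0.25 x 0.75/25) = 0.170 and 1.96 x sqrt(0.25 x 0.75/20) = 0.190, matching the stated 17% and 19%.

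**Step 1: the eligible window.** The limits come from Section 11.3, criterion 5. Excluded: TSH > 1.25 x ULN or TSH < 0.8 x ULN. Eligible: 0.8 x ULN ≤ TSH ≤ 1.25 x ULN. This follows from the text alone and needs no assumption.

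**Step 2: is it corrected anywhere?** The synopsis and Section 11.3 agree word for word, which makes a PDF-reading fault unlikely. Section 10.1.3.1 allows an uncertain or abnormal screening result to be repeated, but it does not waive the limit. Section 25.1 refers to a list of laboratory normal ranges that is held outside these documents.

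**Step 3: how much of the normal range is lost?** Set ULN = 1 and LLN = r. The documents give no value for r, so r is an assumption, varied from 0.05 to 0.5 with 0.6 added to locate the break-even. LLN and ULN are taken as the 2.5th and 97.5th percentiles for the two bell-shaped cases.

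- Uniform within the range: excluded share = (0.8 − r)/(1 − r).
- Normal: mean (1 + r)/2, SD (1 − r)/3.92; excluded share = [P(TSH < 0.8) − 0.025]/0.95.
- Log-normal: the same formula on the log scale, with mean ln(r)/2 and SD −ln(r)/3.92.

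Worked example at r = 0.3:

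- Uniform: 0.5/0.7 = 0.714.
- Normal: mean 0.65, SD 0.1786, z = 0.84, P = 0.7995, share = 0.7745/0.95 = 0.815.
- Log-normal: mean −0.602, SD 0.307, z = (−0.223 + 0.602)/0.307 = 1.23, P = 0.891, share = 0.866/0.95 = 0.912.

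Share of normal-range TSH values that the rule excludes:

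| LLN/ULN | Log-normal | Normal | Uniform |
|---|---|---|---|
| 0.05 | 97.6% | 89.1% | 78.9% |
| 0.1 | 96.6% | 88.1% | 77.8% |
| 0.3 | 91.2% | 81.5% | 71.4% |
| 0.5 | 77.1% | 66.0% | 60.0% |
| 0.6 | 60.3% | 50.0% | 50.0% |

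Under the normal and uniform shapes the share falls to one half only when LLN reaches 0.6 x ULN. Under the log-normal shape it is still 60% there.

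**Step 4: the same population with a floor at 0.8 x LLN.** The eligible window becomes 0.8 x LLN to 1.25 x ULN, which contains the whole normal range, so no in-range value is excluded. Under the log-normal shape, 97.6% (r = 0.05) to 99.3% (r = 0.3) of a reference population is eligible. Under the criterion as written the figures are 3.5% and 10.5%.

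**The case against.** The strongest reply is that this is a drafting slip with almost no analytic consequence.

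- **Intent is clear from the lead-in.** The list covers abnormalities, so an investigator could reasonably read the lower limb as reaching only abnormally low values. That is a fair account of how a site might behave. It does not rescue the number: 0.8 x ULN is not a threshold for abnormally low TSH under any reference range with LLN below 0.8 x ULN.
- **The consequences are not observed.** A site may have asked the sponsor and received a clarification outside these documents, and no TSH values for this population are given. This stands. The size of any screening loss or breach count is unknown.
- **The percentages rest on assumptions.** This also stands. What does not depend on them is the 0.8 to 1.25 x ULN window. That most normal values are excluded holds for any LLN below 0.6 x ULN under the three shapes tried.
- **The analysis barely moves.** The primary endpoint is the incidence of treatment-emergent adverse events in the Safety Analysis Set, which keeps every dosed subject. The Full Analysis Set also ignores eligibility breaches. Only the Per Protocol Set could be touched, and only if the breach is judged to affect efficacy. This stands and limits how serious the point is.
- **An amendment is not free, and may be late.** Section 20.1 requires IRB approval of all but logistical or administrative amendments. SAP Section 3.9.7 already describes what happened in practice during the study, so screening may be finished. In that case only the deviation-review part of the remedy still has an effect.

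**Conclusion.** The concern holds. As written, criterion 5 admits only TSH between 0.8 and 1.25 x ULN, and neither document corrects it. Assuming LLN/ULN between 0.05 and 0.5, it excludes 77% to 98% of normal-range values under a log-normal shape, 66% to 89% under a normal shape and 60% to 79% under a uniform one. That an LLN-based floor was meant is an inference from the lead-in, though a strong one.

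The harm lies in screening, protocol compliance and possibly drug discontinuation. It does not reach the primary safety analysis or the stated precision. Per Protocol membership is exposed only through case-by-case judgement. The deviation listing in SAP Section 3.4.2 covers only subjects excluded from that set, so the planned outputs may not show which reading was applied. It should be fixed, but it does not threaten the trial's main conclusion.

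**What to change.** 1. In criterion 5 of both Section 7 and Section 11.3, replace the lower TSH limit with one tied to the laboratory's lower limit of normal, for example < 0.8 x LLN. The sponsor's clinical team should confirm the multiplier.
2. Add LLN to the abbreviation list in Section 6.
3. For subjects already enrolled, record at the blinded deviation review planned in SAP Section 3.2.1 that a TSH within the laboratory's reference range is not an efficacy-impacting eligibility violation.

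The cost is one line changed in two places, one abbreviation, and one line in the minutes of a meeting already planned. The protocol change needs the usual amendment handling by the IRB and regulators (Sections 20.1 and 24). No extra data or patients are needed. If recruitment has closed, step 3 alone settles the matter for the analysis.

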11.4 Withdrawal of Subjects

A subject may voluntarily withdraw at any time and for any reason. If a subject withdraws, at his or her request or at the request of his or her caregiver or legal representative, the reason(s) must be recorded on the relevant page of the subject's eCRF. Subjects who withdraw from the study prematurely should undergo all end-of-study assessments where possible. It is vital to obtain follow-up data on any subject withdrawn because of an AE. In any case, every effort must be made to undertake protocol-specified safety follow-up procedures. If a subject refuses to continue with study procedures, the reason for refusal should be fully documented in the subject's source document and recorded in the study specific eCRF. Subjects who withdraw from the study prior to completing the final follow-up visit may be replaced at the discretion of Ovid Therapeutics Inc.

